3.2.1.1 Relative day

Relative day for an event will be derived with the date of the first sc infusion of Investigational Medicinal Product (IMP) in MG0004 as reference.

Relative days for an event of measurement occurring before the date of first sc infusion will be prefixed with '-' and are calculated as follows:

$$\text{Relative Day} = [(\text{Event Date} - \text{Date of First Infusion})]$$

Relative days for an event or measurement occurring on or after the date of first sc infusion are calculated as follows:

$$\text{Relative Day} = [(\text{Event Date} - \text{Date of First Infusion}) + 1]$$

For events or measurements occurring after the date of the last sc infusion, relative day will be prefixed with '+' in the data listings and are calculated as follows:

$$\text{Relative Day} = + [(\text{Event Date} - \text{Date of Last Infusion})]$$

There is no relative Day 0. Relative day is not calculated for partial dates in cases where relative day is shown in a participant data listing. In such cases, relative day should be presented as '- -' in the participant data listings.

3.2.2 Study periods

The maximum duration of the study per participant will be approximately 60 weeks, consisting of the following 2 periods:

- Treatment Period: 52 weeks
- Observation Period: 8 weeks

The end of the study is defined as the date of the last visit of the last participant in the study.

The following definitions for starting and entering the study periods will be applied:

- **Treatment Period** starts with the first day of IMP in MG0004 and ends after Week 52 or PEOT assessments. All participants in the Safety Set will be considered to have started the Treatment Period. A participant is considered to have completed the Treatment Period if assessments from Treatment Period Week 52 are completed.
- **Observation Period** starts with one day after the end of the Treatment Period and ends after the final assessments at the End of Study (EOS) visit. Participants with assessment on any Observation Period day are considered to have started the Observation Period. Participants who complete the assessments at the EOS visit will be considered to have completed the

Observation Period. Participants who have a completed status in the study termination case report form (CRF) are considered to have completed the Treatment and Observation Period.

3.2.3 Mapping of assessments performed at Premature End of Treatment Visit

PEOT assessments will be assigned to the next scheduled site visit (following the last scheduled visit that the participant completed prior to PEOT) where each assessment is evaluated as per protocol. This approach means that there is a chance that PEOT data will be mapped to different visits according to the schedule of assessments.

3.3 Definition of Baseline values

If not otherwise stated, Baseline values will be the last available value prior to or on the same date (and same time if time is collected for the individual assessment) of first administration of IMP in MG0004. Scheduled or unscheduled measurements can be used as the Baseline value.

Baseline values for serum or plasma complements and serum cytokines will be the Baseline values determined in MG0003.

Baseline for anti-drug antibody (ADA) for MG0004 should be the last measurement prior to receiving the very first rozanolixizumab (RLZ) infusion across all MG studies. Specifically, baseline for ADA is define as:

- MG0003 ADA baseline if participants randomized to RLZ groups in MG0003;
- MG0004 ADA baseline if participants randomized to placebo in MG0003.

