MG0004 will then evaluate the long-term safety, tolerability, and efficacy of rozanolixizumab over a 52-week Treatment Period. An open-label study with a treatment duration of 52 weeks is considered sufficient to adequately assess long-term safety with rozanolixizumab for the proposed indication. The dose regimen for rozanolixizumab in MG0004 will be the same one that is used in MG0003 and MGC003 (equivalent to approximately [REDACTED]), although the dose may be modified based on interim analysis in MG0003 (Section 4.3). In MG0004, study participants will be rerandomized to 1 of 2 doses of rozanolixizumab, and will be allowed to switch between dose arms at the discretion of the Investigator. MG0004 will therefore allow study participants to switch their dose of study medication on an individual basis. MG0004 also offers study participants the chance to benefit from long-term treatment. MG0004

will conclude with an 8-week Observation Period, which is the anticipated duration of time required for antibodies to return to Baseline levels after rozanolixizumab treatment.

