10.2 Pharmacodynamics

10.2.1 Total serum IgG and IgG subclasses

Total serum IgG concentrations and IgG subclasses will be summarized by first dose received and time point for observed values, change from Baseline, and percentage change from Baseline.

The maximum change from Baseline in total serum IgG (absolute and percentage change) will be reported in the listing and summarized by first dose received. In the event that a change from Baseline in total serum IgG is not observed in a given participant, the maximum change will be reported as the smallest increase from Baseline.

Mean and mean percentage change from Baseline values in total serum IgG will be plotted over time by first dose received with dose groups overlaid on the same plot.

Spaghetti plots will be provided for absolute IgG and percentage change from baseline in IgG over time stratified by first dose received and Baseline bodyweight group (<50kg, 50kg-<70 kg, 70-<100kg, ≥100kg) where the Baseline bodyweight group is multipaneled or overlaying with different colors within each treatment group.

Serum concentrations of total IgG and IgG subclasses will be listed together with concentrations of rozanolixizumab, ADA and NAb sample status and titer, MG-specific autoantibodies, and MG-ADL change from Baseline, as specified in [Section 10.3.2](#).

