10.2.2 MG-specific autoantibodies

MG-specific autoantibodies (anti-MuSK/anti-AChR) will be summarized by first dose received and RLZ total at scheduled visits for observed values, absolute and percentage changes from Baseline. The maximum change from Baseline in MG-specific autoantibodies (absolute and percentage change) will be reported in the listing and summarized for each treatment.

MG-specific autoantibodies will also be summarized at scheduled visit by the participants who are anti-MuSK or anti-AChR autoantibody-positive at the Baseline visit.

Mean absolute and mean percentage change from Baseline values in MG-Specific autoantibodies will be plotted over time by treatment group and RLZ total. Additionally, mean percentage change from Baseline in anti-MuSK, total IgG, MG-ADL, QMG, and MG-C will be plotted by first dose received. The same plot will be repeated for percentage change from Baseline values in anti-AChR.

MG-specific autoantibodies will be listed, together with total IgG, MG-ADL, QMG, MG-C change from Baseline.

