14 AMENDMENT(S) TO THE STATISTICAL ANALYSIS PLAN

14.1 Amendment 1

Rationale for the amendment

This amendment is to apply following changes:

- Adverse event summaries to be consistent with MG0003
- Update definitions of ADA participant categories, and update related analyses
- Minor cosmetic changes

Modifications and changes

Section # and Name	Description of Change	Brief Rationale
General	Added RLZ total to summary tables	To be consistent with MG0003
General	Minor administrative, formatting, and typographical changes have been made.	Updated to provide clarity and be consistent with remainder of SAP.
3.3 Definition of Baseline values	Modified general definition of Baseline values and added Baseline definition for anti-drug antibody.	To consider actual assessment time and add more accurate definition for ADA considering MG0003 treatment effect
3.8 Coding dictionaries	Updated MedDRA and WHODD version	Newer versions were released
4.9 Examination of subgroups	The stratification factors MuSK(+/-) and AChR(+/-) in the subgroup analysis were changed to be based on the values from MG-specific autoantibody assessment taken at Baseline in MG0003.	To be consistent with MG0003
5.1 Subject disposition	Added a table to summarize the number of participants at each visit by treatment group.	Based on DEM3 comment to understand the pattern of dropouts
6.1 Demographics	Age was changed to be the age at the time of MG0003 entry.	To compare age population across MG studies
6.1 Demographics	Added race, ethnicity group and needed rescue therapies in the observation period of MG0003 and entered MG0004	To be consistent with MG0003 and MG0007

6.2 Other Baseline characteristics	Defined MG-ADL cutoff as 5	The cutoff was determined in MG0003
6.4 Prior and concomitant medications	Added definitions of rescue medications	To provide clear definitions of rescue medications in programming
8.2 Adverse events	Reorganized adverse event summaries	To be consistent with MG0003
8.3.1 Potential drug-induced liver injury	Modified PDILI criteria and added new summaries	To be consistent with PSAP
8.4.2 Electrocardiograms	Removed QTcB	QTcB is not of interest
8.4.3.2 Suicidal risk monitoring	Suicidal risk monitoring summary analysis was removed	Listing is enough to provide all information
9.1.1 MG-ADL score	Added COVID-19 free analysis for MG-ADL summary. Added MG-ADL (excluding ocular items) summary.	To evaluate impact of COVID-19 pandemic. To be consistent with MG0003.

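### Changes in IgG, IgG subclasses and MG autoantibodies are measured from MG0004 entry, when early rescue entrants from active MG0003 arms may still be drug-suppressed

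*SAP*

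**What the plan says.** SAP 3.3 gives the default: "Baseline values will be the last available value prior to or on the same date" as the first MG0004 administration. One exception concerns ADA, which takes the "MG0003 ADA baseline if participants randomized to RLZ groups in MG0003" and the MG0004 Baseline for former placebo participants. The SAP amendment log explains the change to this section: "To consider actual assessment time and add more accurate definition for ADA considering MG0003 treatment effect". The only other exception covers complement and cytokines. Total IgG, IgG subclasses and autoantibodies are in neither, and all are sampled at MG0004 Visit 1 (Protocol Table 1-1).

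Under SAP 10.2.1, IgG and its subclasses are "summarized by first dose received and time point for observed values, change from Baseline, and percentage change from Baseline". The same section adds: "The maximum change from Baseline in total serum IgG (absolute and percentage change) will be reported in the listing", and also has it summarized by first dose. Under SAP 10.2.2, autoantibodies "will be summarized by first dose received and RLZ total at scheduled visits for observed values, absolute and percentage changes from Baseline". Neither section splits by MG0003 treatment or by route of entry.

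Protocol 4.1 and SAP 2.3 give two routes into MG0004: completing the MG0003 Observation Period, or needing rescue (other than IVIg or PEX) during it. Protocol 4.2 explains the 8-week Observation Period of MG0004 as one "which is the anticipated duration of time required for antibodies to return to Baseline levels after rozanolixizumab treatment".

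In its estimand text, Protocol Section 3 plans biomarker summaries by first MG0004 dose, both pooled and broken down by the treatment received in MG0003. Protocol 9.3.3.2 lists total IgG and subclasses among the biomarkers and handles the autoantibodies alongside them.

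**The concern.** The drug is designed to lower IgG. A participant who was on active drug in MG0003 and crosses over before recovering starts MG0004 with a low value, so further lowering from that point looks small. Placebo participants and those fully washed out start from their untreated level. Tables by first MG0004 dose average these two kinds of change, and a reader will take the result as the drug's pharmacodynamic effect.

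Three displays are most exposed:

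- **Maximum change in IgG (SAP 10.2.1).** It depends directly on the entry value.
- **Week 60.** Simple recovery can appear as IgG above Baseline in early entrants from active arms.
- **ADA-by-IgG tables and plots (SAP 10.3.2).** ADA category is anchored before the first-ever rozanolixizumab dose, but the IgG change beside it starts at MG0004 entry. Two Baselines meet in one display.

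**Working it through.** The plan gives no figure to reproduce: the study is descriptive, with no testing and no formal sample size. What follows is an illustration.

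**Inputs from the documents.** Protocol 4.3 reports a mean IgG nadir of 3.3 g/L in MG0002, about 70% below Baseline. The implied untreated level is 3.3 / (1 − 0.70) = 11.0 g/L. Protocol 4.2 gives 8 weeks for recovery.

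**Assumptions.** The same nadir is reached in MG0003 and MG0004 at both doses. Recovery, with t in weeks since the last MG0003 dose, is either

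- linear: entry IgG = 3.3 + 7.7 × t/8, or
- exponential, 95% complete at week 8: entry IgG = 11.0 − 7.7 × exp(−kt), with k = −ln(0.05)/8 = 0.374.

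**Participant level.** Reported change at the nadir = (3.3 − entry IgG) / entry IgG. From the untreated level it is −7.7 g/L, or −70%.

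| Weeks since last dose | Entry IgG, linear (g/L) | Reported change | Entry IgG, exponential (g/L) | Reported change |
|---|---|---|---|---|
| 1 | 4.26 | −23% | 5.71 | −42% |
| 2 | 5.22 | −37% | 7.36 | −55% |
| 4 | 7.15 | −54% | 9.28 | −64% |
| 6 | 9.07 | −64% | 10.19 | −68% |
| 8 | 11.0 | −70% | 10.62 | −69% |

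**Arm level.** Let w be the share of the arm made up of rescue entrants from active MG0003 arms, so w = rescue share × 2/3. The two-thirds assumes equal allocation to placebo and two doses in MG0003; the ratio is not stated. All other participants are taken to start untreated. Reported mean = w × (entrant's change) + (1 − w) × (−70%).

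- Rescue share 10%, w = 0.067. Entry at 1 week, linear: 0.067 × 22.6 + 0.933 × 70 = 66.8%. Entry at 6 weeks, exponential: 0.067 × 67.6 + 0.933 × 70 = 69.8%.
- Rescue share 30%, w = 0.20. The same two extremes give 60.5% and 69.5%.
- Rescue share 50%, w = 0.333. They give 54.2% and 69.2%.

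The true value is 70% throughout. Under both curves the error is toward understatement.

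**Protocol against SAP.** The breakdown by MG0003 treatment in Protocol Section 3 does not appear in SAP 10.2.1 or 10.2.2, and SAP 3.9, which lists departures from the protocol, does not mention it. SAP 10.3.2 does repeat several ADA tables by MG0003 treatment, so the variable is available to the analysis.

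**The case against.** The best defence is that an extension-entry Baseline is legitimate. It follows Protocol 9.2 and matches the efficacy Baseline, and as change since MG0004 entry the figures are correct. Observed IgG and autoantibody values are also summarized, absolute IgG is plotted per participant, and the low-IgG abnormality criterion is an absolute threshold. These are Other objectives in a study without testing. All of this stands, and it keeps the point minor. It does not answer the dropped split or the mixed Baselines in the ADA displays.

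Several stronger readings are tempting but unsupported:

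- **That the SAP already corrects complement and cytokines for carry-over.** It does say "Baseline values for serum or plasma complements and serum cytokines will be the Baseline values determined in MG0003". But Protocol Table 1-1 schedules no such sample at Visit 1 and the testing is event-driven, so the lead-in value may be used simply because no entry sample is planned. ADA is the one precedent tied to MG0003 treatment, and ADA has its own reason: pre-existing and treatment-induced antibodies must be told apart.
- **That tetanus titres are equally affected.** Table 1-1 schedules no Visit 1 titre, so the timing of their Baseline, and any suppression, cannot be established.
- **That all reported IgG lowering is understated, or that one dose is favoured.** Placebo entrants are unaffected. Completers are affected little or not at all if the MG0003 Observation Period is also about 8 weeks, a length these documents do not state. Rerandomization 1:1 should balance carry-over between doses in expectation.
- **That 37% and 54% are the size of the effect.** They are the linear-recovery end of a range.

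**Conclusion.** The point holds for change, percentage change and maximum change in total IgG, and for change and percentage change in IgG subclasses and change measures for anti-AChR/anti-MuSK. It holds only for participants from active MG0003 arms who enter before recovering. The mechanism and direction follow from the documents: the default Baseline, the early rescue route and the stated recovery time. The size does not, because rescue share, time since last dose, recovery shape and MG0003 allocation are not given. On the assumptions above, an individual 70% fall could read as anything from 23% (entry at 1 week, linear) to 68% (6 weeks, exponential). An arm mean could read as about 67% to 70% if 10% are rescue entrants, and 54% to 69% if 50% are.

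The undeclared loss of the split by MG0003 treatment rests on the text alone. It is clearest for total IgG and subclasses, which the protocol names as biomarkers. This is a low-priority improvement and does not threaten the primary safety objective.

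**What to change.** 1. Keep the MG0004-entry summaries in SAP 10.2.1 and 10.2.2.
2. Restore the split by MG0003 treatment there, and add a split by route of entry (rescue or completed). Rescue entry is already a demographic variable in SAP 6.1. If the split is deliberately dropped, declare that in SAP 3.9.
3. Add change and percentage change, including maximum change, from the last value before the first-ever rozanolixizumab dose: the MG0003 Baseline for former active arms and the MG0004 Baseline for former placebo. This is the rule SAP 3.3 already uses for ADA.
4. Use that Baseline for IgG in the SAP 10.3.2 displays of IgG change by ADA category or titre, so both quantities share one reference.

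The cost is a few extra tables and a derived Baseline variable, with no new sampling. The lead-in protocol should be checked to confirm that each analyte was measured before the first MG0003 dose.

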3.4 Protocol deviations

Important protocol deviations (IPDs) are deviations from the protocol which potentially could have a meaningful impact on study conduct or on the key safety, or PK/PD outcomes (if applicable) for an individual participant. The criteria for identifying important protocol deviations will be defined within the appropriate protocol-specific document. Important protocol deviations will be reviewed as part of the ongoing data cleaning process and data evaluation.

3.5 Analysis sets

3.5.1 Enrolled Set

The Enrolled Set (ES) will consist of all study participants who sign the informed consent.

3.5.2 Randomized Set

The Randomized Set (RS) will consist of all study participants who are randomized, using the treatment assigned instead of the actual treatment received.

3.5.3 Safety Set

The Safety Set (SS) will consist of all randomized study participants who received at least 1 dose of IMP in this study. Analysis of this set will be according to the treatment the study participants actually received in MG0004, and will be used for the efficacy, demographic, PK/PD and safety analyses. The treatment assignment using SS is described in [Section 3.6](#).

3.6 Treatment assignment and treatment groups

For the analyses using SS by the first dose received, study participants will be grouped according to the dose levels of IMP participants first received [REDACTED] in this study (i.e. before any switching occurs) using the exposure data from CRF. For example, if study participants randomized to IMP [REDACTED] and first received IMP [REDACTED], then these study participants will be allocated to IMP [REDACTED]. If a study participant first received IMP [REDACTED] and then switched to [REDACTED], then the study participant will be allocated to [REDACTED].

For the analyses using SS by the most recent dose received, study participants will be grouped according to the most recent dose level of IMP participants received prior to each visit or the onset of events using the exposure data from CRF. For example, if a study participant first received IMP [REDACTED] and then switched to [REDACTED] prior to Visit 5, then the participant will be allocated to [REDACTED] at Visit 5.

For the efficacy analyses using SS by dose switch during the Treatment Period, study participants will be grouped into dose adjuster or dose non-adjuster. A study participant who receive different dose during the Treatment Period from the randomized dose level will be classified as a dose adjuster, otherwise dose non-adjuster. For example, if a study participant was randomized to and first received IMP [REDACTED] and then switched to [REDACTED], then the study participant will be allocated to dose adjuster.

For the analyses using RS, study participants will be grouped according to the dose levels of IMP to which study participants were randomized.

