The aim of MG0004 is to compare safety (primarily) of long-term treatment of 2 dose levels of rozanolixizumab. Rescue medication is allowed and is expected to be temporary; dose switching (up or down) is also allowed. Using a treatment policy estimand is considered the only viable option to deal with this complexity. Indeed, a hypothetical estimand that appropriately accounted for treatment switching in this study, differing lengths of treatment in MG0004, and differing exposure to rescue medications in both studies would be very assumption-rich. This estimand will be based on the Safety Set (SS).

For all variables, the population is the study participants meeting the protocol-specified inclusion/exclusion criteria. The main intercurrent events are the use of rescue medication during the course of the study, withdrawal due to TEAEs and treatment switching.

All safety variables, biomarkers, and anti-drug antibody (ADA) results will be summarized for the SS classified by first treatment dose received [REDACTED] in this study (ie, before any switching occurs), both with and without subdivision by treatment dose received in MG0003 (placebo or [REDACTED]).

Efficacy variables will be summarized using a ‘treatment policy’ approach as follows:

- Participant-level outcome: The given variable and time point being summarized (eg, value of MG-ADL at Week 5).
- Population-level summary measure: For categorical variables, unadjusted proportions by first treatment received and, for continuous variables, unadjusted means by first treatment received.

Missing values will not be imputed.

Further details will be provided in the Statistical Analysis Plan (SAP).

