4.2 Scientific rationale for study design

The lead-in studies, MG0003 and MGC003, will evaluate the efficacy, safety, and tolerability of rozanolixizumab compared with placebo in study participants with generalized MG who are treated with study medication over a [REDACTED] at [REDACTED]. Study participants in the lead-in studies will have generalized MG, as evidenced by the presence of anti-AChR or anti-MuSK antibodies. Additionally, study participants in the lead-in studies will have moderate to severe symptoms of MG and should be under consideration for IVIg or PEX therapy, indicating that they are in need of additional therapeutic intervention.

Study participants in MG0003 or MGC003 will be randomized to receive either placebo or 1 of 2 doses of rozanolixizumab. Study participants in MG0003 or MGC003 who require rescue medication (other than IVIg or PEX) during the Observation Period will be invited to be rerandomized in MG0004: this will offer all study participants, even those previously treated with placebo, a chance to be treated with rozanolixizumab. Rerandomization in MG0004 is applied to account for the limited efficacy information on the [REDACTED] dose. Due to the open-label design of MG0004, study participants are allowed to switch dose at the Investigator's discretion during the course of the study (dose modification recommendations for safety are provided in Section 6.6). Study participants developing TEAEs could be switched to a dose equivalent to [REDACTED] and study participants experiencing symptom worsening can be switched to a dose equivalent to [REDACTED].

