6.6 Dose modification

Study participants will be allowed to switch dose arms for tolerability and efficacy reasons, as well as bodyweight changes at the discretion of the Investigator after the first dose of rozanolixizumab. However, when possible, the dose assigned at randomization should be maintained for at least 6 weeks, unless a dose modification is required earlier for tolerability or efficacy reasons. If a dose adjustment is made, the Investigator should encourage study

participants to stay on the modified dose for at least 6 weeks, unless further dose adjustments or discontinuation of study medication is required for the safety of the study participant.

Study participants who experience any AEs that meet the study medication discontinuation criteria (Section 7.1 and Section 0) should have rozanolixizumab discontinued. Study participants in the [REDACTED] cohort who experience a possibly related toxicity other than those that met the study drug discontinuation criteria as defined in Section 7.1 and Section 0 are allowed to switch to [REDACTED] at the Investigator's discretion. Recommended dose modifications due to toxicities may include (but not exclusive):

- Moderate to severe headaches that are considered to be related to rozanolixizumab (Section 10.20.1)
- Moderate to severe GI disturbances that are considered to be related to rozanolixizumab
- Moderate to severe toxicities (\geq Grade 2 as defined by CTCAE, version 5) for which rozanolixizumab cannot be excluded as a cause
- Recurrent hypogammaglobulinemia with a serum total IgG $<2\text{g/L}$

The date and reason for dose change of rozanolixizumab is to be recorded on each study participant's eCRF.

If any safety concerns are identified in MG0003 (ie, as recommended by the IDMC), or if one of the dose arms is determined to be futile and is discontinued in MG0003, corresponding changes may be made in the MG0004 dosing scheme. A study participant on a dose that was discontinued will switch doses immediately.

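### The SAP 3.6 dose adjuster / non-adjuster grouping labels participants by a later, partly outcome-driven event, so its contrast can show an efficacy gap when dose has no effect

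*SAP*

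**What the plan says.** SAP 3.6 sets out several ways of grouping participants. One is introduced with "For the efficacy analyses using SS by dose switch during the Treatment Period", and under its rule those who "receive different dose during the Treatment Period from the randomized dose level will be classified as a dose adjuster, otherwise dose non-adjuster". The comparison is with the randomized dose. The rule has no switch date, landmark or minimum follow-up. Another grouping in the same section, by contrast, is time-updated and uses the "most recent dose level of IMP participants received prior to each visit or the onset of events".

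The protocol explains how a dose comes to change. Its estimand text (Section 3) says that "dose switching (up or down) is also allowed". It names treatment switching among the main intercurrent events, adopts a treatment policy approach, and summarises efficacy by first treatment received. Section 4.2 gives TEAEs as one trigger and says "study participants experiencing symptom worsening can be switched to a dose equivalent to" a level redacted in the public copy. Under Section 6.6 participants are "allowed to switch dose arms for tolerability and efficacy reasons, as well as bodyweight changes at the discretion of the Investigator". That section adds that, when possible, "the dose assigned at randomization should be maintained for at least 6 weeks", with an exception for earlier changes needed for tolerability or efficacy. A dose arm dropped after the MG0003 interim analysis would also move participants (Protocol 4.1, SAP 2.3).

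Treatment lasts up to 52 weeks, but participants may transfer to MG0007 after a minimum of 6 visits (Protocol 4.1, SAP 2.3). SAP 9 makes first dose received the default efficacy grouping and plans no testing.

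**The concern.** A table of MG-ADL change for non-adjusters would naturally be read as efficacy in participants who stayed on their assigned dose. The rule does not support that reading, for five reasons.

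1. Group membership depends on something that happens after baseline, and worsening or TEAEs are among the stated triggers.
2. The label looks forward. Someone who first switches at Week 40 is an adjuster in a Week 5 summary.
3. Opportunity is unequal. A participant who leaves for MG0007 after 6 visits has far less time to switch than one treated for 52 weeks.
4. Switches for worsening, for tolerability and after closure of an arm share one label. Whether a change of bodyweight tier counts as a different dose is not stated.
5. Because the reference is the randomized dose, a participant given the other dose from the start and kept on it is an adjuster who never switched. The first-dose grouping in the same section places that participant by the dose actually given.

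At stake is a supplementary comparison in an open-label study whose endpoints and visits are not yet fixed, and whose result could be taken as evidence about dose.

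**Working it through.** The documents give no sample size calculation, test, switch rate or SD for this point, so there is no plan figure to reproduce. Every numerical input below is assumed except three time points: the 6-week guidance, the 6-visit minimum and the 52-week maximum. The purpose is to show which way the rule can push, not to predict this trial.

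**Check 1: opportunity to switch (unrelated to response).** Let h be the weekly switch rate, with switching starting after Week 6. Then P(switch) = 1 − exp(−h × weeks at risk). Assume a fraction f leaves at Week 8 and the rest stay 52 weeks. With h = 1% and f = 50%:

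- Week 8 leavers: 1 − exp(−0.01 × 2) = 2.0%
- 52-week stayers: 1 − exp(−0.01 × 46) = 36.9%
- Leavers among non-adjusters: 0.5 × 0.980 / (0.5 × 0.980 + 0.5 × 0.631) = 60.8%
- Leavers among adjusters: 0.5 × 0.0198 / (0.5 × 0.0198 + 0.5 × 0.369) = 5.1%

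Over h = 0.5–2% and f = 30–70%, leavers make up 35–85% of non-adjusters and 2–13% of adjusters. If switching can start at Week 0, which the exception in Protocol 6.6 permits, the adjuster figure becomes 7–35%. The non-adjuster figure is unchanged, because the difference in time at risk is 44 weeks either way.

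**Check 2: selection on response, closed form.** Let MG-ADL change X be normal with mean −2.5 and SD 3, and let switching have no effect. A poor response is X ≥ −1.

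- P(poor) = P(Z ≥ 0.5) = 0.3085
- Contribution of poor responders to the mean: −2.5 × 0.3085 + 3 × 0.3521 = 0.285
- Contribution of the others: −2.5 − 0.285 = −2.785

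Let a and b be the switch probabilities for poor and other responders. The adjuster mean is (0.285a − 2.785b) / (0.3085a + 0.6915b). The non-adjuster mean replaces a and b by 1 − a and 1 − b.

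| a, b | Non-adjuster mean | Adjuster mean | Non-adjusters look |
|---|---|---|---|
| 0.5, 0.1 | −3.04 | −0.61 | better by 2.4 |
| 0.3, 0.1 | −2.75 | −1.19 | better by 1.6 |
| 0.2, 0.2 | −2.50 | −2.50 | the same |
| 0.1, 0.3 | −2.22 | −3.39 | worse by 1.2 |

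This set-up exaggerates somewhat, because the score that triggers the switch is the score then averaged. It also has no time axis.

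**Check 3: the forward-looking label, by simulation.** Underlying MG-ADL change has mean −2.5 and SD 2.5, plus visit noise of SD 2. There is no dose effect. The switch rate is 1–2% per week after Week 6, and 0–50% of participants leave at Week 8. The hazard ratio (HR) is per SD of worse response. Results at Week 5, before any simulated participant has switched:

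| HR | 1%/week, 50% leave early: non-adjuster / adjuster | 2%/week, none leave early: non-adjuster / adjuster |
|---|---|---|
| 1.00 | −2.49 / −2.48 | −2.49 / −2.49 |
| 1.65 | −2.73 / −1.59 | −3.54 / −1.82 |
| 2.72 | −2.94 / −0.97 | −4.11 / −1.41 |
| 0.61 | −2.26 / −3.42 | −1.46 / −3.19 |

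Across all runs, non-adjusters look better by 1.1 to 2.7 points when worse responders switch more. They look worse by 1.1 to 1.7 when better responders do, and the gap is about zero when switching is unrelated to response. In the 1%, 50%, HR 1 run, 92% of eventual adjusters had not yet switched at Week 9, 53% at Week 25 and 13% at Week 45. Most early-visit adjusters are therefore still on their original dose.

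**The case against.** The strongest reply is that nothing listed in the SAP uses this grouping. The grouped summaries in SAP 9.1 and 9.2 are by first dose received, and neither the subgroup section (4.9) nor Section 11 mentions adjusters. The primary objective is safety, efficacy is descriptive, and no decision in the documents rests on the split. All of that stands and limits the weight of the point. It does not remove it: SAP 3.6 says efficacy analyses by dose switch are intended, and leaves their endpoints and visits open.

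Three stronger readings are tempting and should not be adopted.

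- A reader might infer that non-adjusters are enriched for good responders. That holds only if worsening drives switching. Tolerability, bodyweight and arm-closure switches imply no such direction and could reverse it.
- A reader might infer that participants who leave after 6 visits are almost all non-adjusters. The 6-week guidance has an exception for tolerability and efficacy, 6 visits is a minimum rather than a fixed exit, and the share leaving early is not given. Less opportunity to switch is supported; near-exclusivity is not.
- A reader might infer that SAP 3.9 should have recorded a departure from the protocol. That section lists changes to protocol-defined analyses, and none is replaced here, because the first-dose summaries remain.

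It is also fair to say that indexing by visit does not cure everything. Participants not yet switched at Week 40 are still selected by outcome and retention.

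**Conclusion.** The point holds as a limited one. The grouping is poorly defined for any efficacy contrast: it uses future information, confounds switching with length of follow-up, mixes reasons and directions, and misclassifies anyone kept on a non-randomized first dose. These defects follow from the text alone.

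The size and sign of any resulting gap do not. The assumed scenarios span non-adjusters looking 2.7 points better to 1.7 points worse on MG-ADL at Week 5. Protocol 8.1.3.1 treats a 2-point improvement as clinical improvement, so an artefact of relevant size is possible in either direction. These figures rest on assumed switch rates, SDs, early-leaving shares and links between switching and response, and are not estimates for MG0004. The by-first-dose efficacy summaries are not affected.

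**What to change.** In SAP 3.6:

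- Define switch status by visit: not yet switched at every visit before the first change, switched afterwards. Judge it against the first dose received.
- Split it by direction and by recorded reason, and state whether a bodyweight-tier change counts.
- For switchers, report MG-ADL, QMG and MG-C at Baseline, at the last visit before the switch and at visits after it.
- Do not present the whole-period adjuster versus non-adjuster contrast at visits before the switch.
- Name the outputs that use the grouping and show follow-up time per group.
- Label the comparison descriptive and non-causal, because visit indexing removes the use of future information and the misclassification but not outcome-driven selection.

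The cost is SAP wording and modest re-programming of a supplementary summary. No new data are needed: Protocol 6.6 already requires the date and reason of each dose change in the eCRF, and the three scores are collected under the Schedule of Activities.
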